| 10.1 | Statistical Analyses of Primary Pharmacokinetic Endpoints | 12 |
| 10.2 | Pharmacokinetic Methods | 13 |
| 10.2.1 | Pharmacokinetic Analysis..... | 13 |
| 10.2.2 | Handling of Data..... | 13 |
| 10.2.3 | Calculation of descriptive statistics | 14 |
| 11 | Pharmacodynamic Analyses..... | 14 |
| 12 | Pharmacogenomic Analyses | 15 |
| 13 | Interim Analysis..... | 15 |
| 14 | Changes in Planned Analysis | 15 |
| 15 | References..... | 16 |

List of Appendices

| | | |
|------------|------------------------------------|----|
| Appendix 1 | List of Summary Tables..... | 17 |
| Appendix 2 | List of Subject Data Listings..... | 19 |

List of Abbreviations and Definition of Terms

| Abbreviation | Definition |
|----------------------------|--|
| AE | Adverse event |
| BE | Bioequivalence |
| BMI | Body mass index |
| C-SSRS | Columbia-Suicide Severity Rating Scale |
| ECG | Electrocardiogram |
| IMP | Investigational medicinal product |
| LLOQ | Lower limit of quantitation |
| MedDRA | Medical Dictionary for Regulatory Activities |
| OD | Orally disintegrating |
| PK | Pharmacokinetic |
| QTc | Corrected QT interval |
| QTcB | QT interval corrected for heart rate by Bazett's formula |
| QTcF | QT interval corrected for heart rate by Fridericia's formula |
| SAE | Serious adverse event |
| SAP | Statistical analysis plan |
| SD | Standard deviation |
| TEAE | Treatment-emergent adverse event |
| WHODD | World Health Organization Drug Dictionary |
| AUC | Area under the concentration-time curve |
| AUC _∞ | Area under the concentration-time curve from time zero to infinity |
| AUC _t | Area under the concentration-time curve calculated to the last observable concentration at time t |
| AUC_%Extrap | Ratio of area under the concentration-time curve from t _{last} to infinity versus AUC _∞ |
| CL/F | Apparent clearance of drug from plasma after extravascular administration |
| CL/F/BW | Apparent clearance of drug from plasma after extravascular administration per body weight |
| C _{max} | Maximum (peak) plasma concentration of the drug |
| λ _z | Terminal elimination rate constant |
| λ _z (Rsq) | Goodness of fit statistic for the terminal elimination phase, adjusted for the number of points used in the estimation of λ _z |
| λ _z (point) | Number of points used in computing λ _z |
| λ _z (upper) | Upper limit of time for values to be included in the calculation of λ _z |
| λ _z (lower) | Lower limit on time for values to be included in the calculation of λ _z |
| t _{1/2,z} | Terminal-phase elimination half-life |
| t _{last} | Time of the last measurable concentration |
| t _{max} | Time to maximum (peak) plasma concentration |

1 Introduction

This statistical analysis plan (SAP) describes the statistical methodology and data analysis algorithms and conventions to be applied for statistical analysis in 331-14-002 trial.

2 Trial Objectives

The purpose of the present trial is to investigate the bioequivalence of brexpiprazole ODT 2 mg and brexpiprazole conventional tablet 2 mg.

3 Trial Design

3.1 Type/Design of Trial

This is a single center, open-label, randomized, 3-arm, 3-way crossover trial in 21 healthy adult male subjects. Subjects will be hospitalized to the trial site 3 times during the trial (Days -1 to 8, Days 20 to 28, and Days 40 to 48) and will be discharged at the end of each period of hospitalization (on Days 8, 28, and 48) after completion of safety evaluation and blood collection for pharmacokinetic assessment.

[figure not shown]
A 2-mg dose of brexpiprazole will be administered to each subject as either an ODT or a conventional tablet on Days 1, 21, and 41, and ODT will be administered either with water or without water, according to the randomized administration schedule.

Subjects randomized to Sequence 1 will receive an ODT without water on Day 1, a conventional tablet on Day 21, and an ODT with water on Day 41.

Subjects randomized to Sequence 2 will receive an ODT with water on Day 1, an ODT without water on Day 21, and a conventional tablet on Day 41.

Subjects randomized to Sequence 3 will receive a conventional tablet on Day 1, an ODT with water on Day 21, and an ODT without water on Day 41.

The trial design schematic is shown in [Figure 3-1](#).

Brex = brexpiprazole; ODT = orally disintegrating tablet

Figure 3-1
Trial Design

3.2 Trial Treatments

3.2.1 Brexpiprazole ODTs (Investigational Medicinal Product)

Subjects will receive one 2-mg brexpiprazole ODT with or without 150 mL of ordinary-temperature water. When administered without water, the subject will be instructed to place the tablet directly on the tongue and keep it there until it disintegrates completely before swallowing. Compliance will be ensured by a mouth check.

All doses will be administered after fasting for at least 10 hours and no food will be allowed until 4 hours postdose. Except as part of the dosing procedure, water will be restricted from 1 hour prior to dosing until 2 hours postdose.

3.2.2 Brexpiprazole Conventional Tablets

Subjects will receive one 2-mg brexpiprazole conventional tablet with 150 mL of ordinary-temperature water. Compliance will be ensured by a mouth check. The IMP will be administered after fasting for at least 10 hours and no food will be allowed until 4 hours postdose. Except as part of the dosing procedure, water will be restricted from 1 hour prior to dosing until 2 hours postdose.

3.3 Trial Population

A total of 21 healthy male subjects at least 20 years of age and below 40 years of age, will be enrolled.

3.4 Trial Visit Window

Nominal time points will be used for summary of safety parameters and plasma concentration. The examinations on withdrawal and unscheduled visits will be not used in the analyses and will be provided in the listings.

4 Sample Size

Based on the BE Guideline¹, the sample size was calculated so that the 90% confidence intervals of geometric mean ratios for brexpiprazole C_{max} and AUC_t between ODT (with or without water) and conventional tablet would fall within the bioequivalence range of 0.8 to 1.25.

In a brexpiprazole 4-mg ODT BA study conducted in Japan (331-102-00019) and brexpiprazole bioequivalence studies conducted outside Japan (331-10-243 and 331-13-209), the within-subject variance for natural log-transformed C_{max} and AUC_t values was greatest for C_{max} in Trial 331-13-209 (at 0.035).

Assuming a geometric mean ratio of 1.0 for brexpiprazole C_{max} between ODT (with and without water) and conventional tablet, and a within-subject variance of 0.035 for natural log-transformed C_{max} , to achieve at least 90% power will require 6 subjects in each sequence, 18 in total. Considering the possibility of some subjects being excluded from analysis due to discontinuation, etc, the number of subjects was set as 7 for each sequence and 21 in total.

4.1 Judgment for Conduct of Add-on Subject Study

If bioequivalence cannot be demonstrated in the initial study because of an insufficient number of subjects, an add-on subject study can be performed in accordance with this protocol.

The add-on subject study will be performed using not less than half the number of subjects in the initial study. No add-on subject study will be performed in the following cases:

- 1) If the results of the initial study show that the point estimates of the geometric mean ratios for AUC_t and C_{max} between ODT and conventional tablet do not fall within the range of 0.8 to 1.25, and
- 2) If the required number of subjects for the add-on subject study estimated from the results of the initial study is considered to be a sample size that is ethically or scientifically infeasible.

5 Statistical Analysis Sets

5.1.1 Bioequivalence Analysis Set

All subjects who provided C_{max} or AUC_t through Period 1, Period 2, and Period 3

5.1.2 Safety Population

All subjects who received at least one dose of IMP

5.1.3 Handling of Missing Data

There will be no imputation for missing data.

6 Primary and Secondary Outcome Variables

6.1 Primary Outcome Variables

C_{max} and AUC_t of brexpiprazole

6.2 Secondary Outcome Variables

- 1) Plasma concentration-time profiles of brexpiprazole
- 2) Brexpiprazole AUC_∞, t_{max}, λ_z, AUC_%Extrap, t_{1/2,z}, CL/F, CL/F/BW, and t_{last}

7 Disposition and Demographic Analysis

7.1 Subject Disposition

The number of screened subjects will be presented. The number and percentage of randomized subjects, completed subjects, and discontinued subjects will be presented by sequence. The number and percentage of discontinued subjects by primary reason for discontinuation will also be presented by sequence. The denominators of percentages will be randomized subjects.

The number and percentage of subjects included in each analysis set will be provided by sequence for the randomized subjects.

7.2 Demographic and Baseline Characteristics

For the bioequivalence analysis set and safety analysis set, the descriptive statistics (n, mean, SD, min, median and max) of age, height, weight (screening period) and BMI will be presented overall and by sequence. The frequency distribution of gender, race, ethnicity, country, medical history and current symptoms will be presented overall and by sequence.

7.3 Treatment Compliance

Not applicable.

7.4 Prior and Concomitant Medication

The medications will be coded by World Health Organization Drug Dictionary (WHODD) version March 1, 2019 Global. The previous and concomitant medications will be listed.

7.5 Protocol Deviations

The major protocol deviations will be listed.

8 Efficacy Analyses

Not applicable.

9 Safety Analyses

Safety analysis will be conducted upon the safety analysis set for each formulation and administration method (conventional tablet, ODT without water, ODT with water). Baseline is defined as the last measurement immediately before each dosing (for 12-lead ECG parameters, the mean value of three measurements on the day before IMP administration will be used).

9.1 Extent of Exposure

Subjects who received the IMP will be summarized by each formulation and administration method.

9.2 Adverse Events

Medical Dictionary for Regulatory Activities (MedDRA) version 22.0 will be used to code AEs. TEAEs in each period are defined as adverse events occurred on or after the IMP administration in each period to before the IMP administration in next period or the end of study. If multiple occurrences of the same event are observed in the same subject during the same period, the highest severity will be used for analysis.

The incidence of the following events will be summarized by system organ class, preferred term (the denominators will be subjects who administered by each formulation and administration method).

- TEAEs
- TEAEs by severity

The incidence of the following events will be summarized (the denominators will be subjects who administered by each formulation and administration method).

- TEAEs with an outcome of death
- Serious TEAEs
- TEAEs leading to discontinuation of the IMP

TEAEs potentially causally related to the IMP will also be summarized in the same way.

9.3 Clinical Laboratory Data

For each clinical laboratory parameter except for qualitative urinalysis, the descriptive statistics of measured values and of changes from baseline will be calculated by time point. For qualitative parameters of clinical laboratory urinalysis, shift tables versus baseline at each time point will be produced. For the clinical laboratory parameters except for qualitative urinalysis, measured values will be classified as Within Reference Range,

Lower Than Reference Range, and More Than Reference Range, using the reference range of the trial site, and shift tables versus baseline at each time point will be produced.

9.4 Vital Sign Data

For each vital sign, the descriptive statistics of measured values and of changes from baseline will be presented by time point.

9.5 Physical Examination Data

For physical examination, listing of physical findings will be presented by each subject.

9.6 Electrocardiogram Data

For each 12-lead ECG parameter, the descriptive statistics of measured values and of changes from baseline will be calculated by time point. For 12-lead ECG assessment of normality/abnormality, shift tables versus baseline at each time point will be produced. For QTcF and QTcB, categorical analysis of measured values and of changes from baseline at each time point will be performed to calculate the number and percentage of subjects. The number and percentage of subjects with actual measurements of corrected QT interval (QTcF, QTcB) at each time point being > 450 msec, > 480 msec, and > 500 msec will be determined. The number and percentage of subjects with changes from baseline being > 30 msec and > 60 msec will be also determined.

9.7 Other Safety Data

9.7.1.1 Body Weight

For body weight, the descriptive statistics of measured values and of changes from baseline will be presented.

9.7.1.2 The Columbia-Suicide Severity Rating Scale

C-SSRS data for individual subjects will be listed.

10 Pharmacokinetic Analyses

10.1 Statistical Analyses of Primary Pharmacokinetic Endpoints

The following analysis will be performed on the bioequivalence analysis set:

The C_{max} and AUC_t of brexpiprazole will be analyzed using the natural log-transformed values in a mixed effect model with sequence (1, 2, and 3), formulation and administration method (conventional tablet, ODT without water, ODT with water), and period (Period 1, Period 2, and Period 3) as fixed effects and the subjects within each

sequence as a random effect. The Kenward–Roger method will be used to estimate the degrees of freedom in the mixed effect model analysis. The 90% confidence intervals of geometric mean ratios for brexpiprazole C_{\max} and AUC_t between ODT (with or without water) and conventional tablet will be calculated. If the 90% confidence intervals are within the range of 0.8 to 1.25, the 2 formulations and administration methods will be judged to be bioequivalent.

If an add-on subject study is conducted, bioequivalence will be assessed on the same basis from the result of combining the initial study and the add-on subject study by including study as a fixed effect in the above mixed effect model.

If there are any subjects who had no evaluable parameters through Period 1, Period 2, and Period 3, analysis in which those subjects are included will be performed.

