7.7 Judgement for Conduct of Add-on Subject Study

If bioequivalence cannot be demonstrated in the initial study because of an insufficient number of subjects, an add-on subject study can be performed in accordance with this protocol.

The add-on subject study will be performed using not less than half the number of subjects in the initial study. No add-on subject study will be performed in the following cases:

- 1) If the results of the initial study show that the point estimates of the geometric mean ratios for AUC_t and C_{max} between ODT and conventional tablet do not fall within the range of 0.8 to 1.25, and
- 2) If the required number of subjects for the add-on subject study estimated from the results of the initial study is considered to be a sample size that is ethically or scientifically infeasible.

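### If an add-on study is run, the pooled model should allow period effects to differ by study; the planned study term alone does not, and the fix is cheap

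*SAP*

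**What the plan says.** The base model in Protocol 7.4 and SAP 10.1 is a mixed model for log Cmax and log AUCt. Its fixed effects are sequence, formulation/administration method and "period (Period 1, Period 2, and Period 3) as fixed effects and the subjects within each" "sequence as a random effect". For a pooled analysis of the initial and add-on studies, both documents change it only "by including study as a fixed effect in the above mixed effect model". Neither names a study-by-period term or nests period in study, so Periods 1 to 3 keep one set of effects for both studies.

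The add-on is triggered by the initial result: "If bioequivalence cannot be demonstrated in the initial study because of an insufficient number of subjects" (SAP 4.1; also Protocol 7.7). It therefore runs later. On its size: "The add-on subject study will be performed using not less than half the number of subjects in the initial study".

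The primary analysis set is "All subjects who provided C_{max} or AUC_t through Period 1, Period 2, and Period 3" (SAP 5.1.1), which I read as complete cases. For subjects outside it, a further "analysis in which those subjects are included will be performed" (table BE-1.2 in SAP Appendix 1). The decision rule for the pooled data is the same as for the initial study: "If the 90% confidence intervals are within the range of 0.8 to 1.25".

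**The concern.** In a crossover, the ODT/tablet ratio comes from differences within subjects. A subject belongs to one study only, so a study main effect shifts all three of his values equally and leaves his differences unchanged. What can disturb those differences is a period effect that is not the same in the two studies. The add-on's three periods are different calendar occasions from the initial study's, yet the pooled model gives them common effects.

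Any mismatch goes into the residual variance and so into the width of the confidence intervals. If sequence counts are unequal within the studies, part of it also goes into the ratio. The pooled analysis gives the final bioequivalence decision after a failed first look, where a limit may lie close to 0.80 or 1.25 and avoidable width or bias counts most.

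**Working it through.** **Inputs from the documents.** Within-subject variance of log Cmax 0.035, ratio 1.0, 18 evaluable subjects for at least 90% power, 21 enrolled at 7 per sequence (Protocol 7.1, SAP 4); 90% interval within 0.8 to 1.25; add-on at least half of 21 = 10.5, so at least 11.

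**Assumptions.** The size of any period-by-study difference, the exact add-on size and the losses per sequence. The documents give none of these.

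**The plan's sample size reproduces.** With SE = √(2 × 0.035/n) and 2n − 4 degrees of freedom, exact power for one comparison at ratio 1.0 is 87.5% at n = 15 and 93.7% at n = 18. So 18 is the smallest multiple of 3 that reaches 90%. This does not bear on the point.

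**Does the study term touch the comparison?** One simulated complete data set was fitted (21 + 12 subjects, add-on period effects shifted by −0.1, 0, +0.1 on the log scale):

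| Model | ODT − tablet estimates | SE | Residual variance | Between-subject variance |
|---|---|---|---|---|
| No study term | 0.061713; 0.011416 | 0.041842 | 0.02889 | 0.1465 |
| Study main effect (as planned) | 0.061713; 0.011416 | 0.041842 | 0.02889 | 0.0911 |
| Study and study-by-period | 0.061713; 0.011416 | 0.038676 | 0.02468 | 0.0925 |

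The study term changes only the between-subject variance. With incomplete subjects it does not cancel fully: in a simulated set with three missing period values and a study shift of 0.5 log units, the estimates moved from 0.0327 to 0.0338 and from 0.0673 to 0.0687.

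**Effect on interval width, balanced sequences.** The unmodelled sum of squares is n₁n₂/(n₁ + n₂) × Σd², where d are the period-by-study differences (summing to zero), spread over 2(n₁ + n₂) − 4 degrees of freedom. For 21 + 12 and d = −0.1, 0, +0.1: (252/33) × 0.02 = 0.1527; 0.1527/62 = 0.0025; expected residual 0.035 + 0.0025 = 0.0375; width factor √(0.03746/0.035) = 1.035. At ±0.05 the factor is 1.009 and at ±0.2 it is 1.132.

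**Effect on the decision.** Simulation with 20 + 11 subjects (7/7/6 and 4/4/3) and variance 0.035. Shifts apply to add-on Periods 2 and 3, relative to the initial study. Entries are the probability that both Cmax intervals pass, common versus nested periods:

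| Assumed shift | Ratio 0.93 | Ratio 0.98 | Ratio 1.0 |
|---|---|---|---|
| +10%/−10% | 86.8% vs 88.0% | 98.7% vs 98.9% | 99.3% vs 99.5% |
| +20%/+10% | 86.2% vs 88.0% | not tabulated | 99.4% vs 99.5% |
| +20%/−20% | 82.6% vs 88.0% | 98.1% vs 99.0% | 98.9% vs 99.5% |

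With no shift, at ratio 0.93, the figures are 87.9% and 88.0%, equal within simulation error. All are unconditional. Given a failed first look the gap is larger (ratio 1.0, +10%/−10%: about 92.5% against about 94%), but only about 7% of trials fail at that ratio.

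**AUCt.** The variance can be back-calculated from Protocol 1.2.2. For ODT without water the interval 0.9549 to 1.0575 has log half-width 0.0510. With n = 17 and t = 1.697 on 30 degrees of freedom, SE = 0.0301 and variance = 0.0301² × 17/2 = 0.0077, or about 0.008. With 21 + 11 subjects and +10%/−10%, common periods give a half-width of 0.0425 against 0.0373 nested, 14% wider. The pass probability is 100% under both models, at ratios 1.0 and 0.93.

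**Bias with common periods, shifts of 10%.**
- 7/7/7 + 4/4/4: zero.
- 7/7/7 + 4/4/3: about 0.2% for +10%/−10% in Periods 2 and 3; up to 0.4% when the shift is −0.1, 0, +0.1.
- 7/7/5 + 5/2/4 (illustrative, severe): −1.3% for ODT without water at +10%/−10%; reversing the shift reverses the sign.

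Nesting period in study removes the bias in each case.

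**The case against.** The strongest reply is that nothing in the documents shows period effects differing between studies. A constant difference in level between the studies is already removed by the subject and study terms; only a difference that changes from period to period does harm. One site, inpatient fasted single dosing and a 20-day washout all limit that. The protocol assumes a ratio of 1.0, and the earlier ODT study (another formulation) gave Cmax ratios of 0.979 and 1.024, where the gain from nesting is under 1 point. The pooled model is prespecified identically in both documents. All of this stands and limits the point to a refinement.

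Three stronger readings are tempting but not supported:
- **That the study term is useless.** It absorbs level differences between cohorts and retains some effect in the analysis with incomplete subjects. It does no harm.
- **That an add-on must be unbalanced because 11 does not divide by 3.** The rule sets a minimum; 12 subjects at 4/4/4 is allowed. Some imbalance from losses is plausible, since withdrawals after first dosing are not replaced (Protocol 3.3.1) and early vomiting removes data (SAP 10.2.2), but 7/7/5 + 5/2/4 is only an illustration.
- **That common periods raise the risk of a false bioequivalence claim.** With balanced sequences they only widen the interval, which makes the claim harder. In the severe illustration with the shift reversed and a true ratio of exactly 0.80, the false-pass rate for ODT without water was 7.6% against about 5% nested. That needs both the constructed imbalance and an adverse shift.

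Nor do the documents say how samples are grouped for assay, so assay batches cannot be cited as a cause of period differences.

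**Conclusion.** The point holds as a cheap improvement to a contingent analysis. It follows from the model as written that, in complete cases, the added study term leaves the ODT/tablet estimates and standard errors unchanged and that period effects are constrained to be equal across the two studies. The cost of that constraint depends on differences the documents do not quantify. Under the shifts assumed here it is about 1 to 5 points of pass probability when the true Cmax ratio is 0.93, under 1 point near 1.0, and nothing for AUCt decisions. Bias is zero with balanced sequences and a few tenths of a percent with one subject short at 10% shifts. It reaches about 1.3% only with the severe imbalance at those shifts. If no add-on is run, the point has no effect.

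**What to change.** In Protocol 7.4 and SAP 10.1, write the pooled model with fixed effects for study, sequence, formulation/administration method and period within study (period plus study-by-period), and with subject within sequence and study as the random effect. Settle this before the initial results are seen, because adding the term after a failed first look would be open to challenge.

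The cost is one line of text and 2 residual degrees of freedom. For 21 + 12 subjects they go from 62 to 60 and the t critical value from 1.6698 to 1.6706. If period effects do not differ, the loss of power is under 0.1 point.
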